10.3.2.3 Assessment of Potentially Clinical Significant Laboratory Variables

The criteria for potentially clinically significant laboratory values will be determined by OMERACT criteria of Grade 3 or 4. For creatine phosphokinase and creatinine, NCI CTC criteria will be used.

The number and percentage of subjects meeting the criteria for potentially clinically significant laboratory values will be summarized by "as treated" treatment group and overall.

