  - HCV: HCV ribonucleic acid (RNA) detectable in any subject with anti-HCV antibody (HCV Ab).
  - HIV: confirmed positive anti-HIV antibody (HIV Ab) test.
9. Subject has active TB or meets TB exclusionary parameters (refer to Section 5.3.1.1 for specific requirements for TB testing).
  10. Systemic use of known strong cytochrome P450 (CYP)3A inhibitors or strong CYP3A inducers from Screening through the end of the study (refer to Table 1 for examples of commonly used strong CYP3A inhibitors and inducers).
  11. Receipt of any live vaccine within 4 weeks prior to the first dose of study drug, or expected need of live vaccination during study participation including at least 4 weeks after the last dose of oral study drug and including at least 70 days after the last dose of subcutaneous study drug.
  12. History of any malignancy except for successfully treated NMSC or localized carcinoma in situ of the cervix.
  13. History of clinically significant (per Investigator's judgment) drug or alcohol abuse within the last 6 months.
  14. History of gastrointestinal perforation (other than appendicitis or penetrating injury), diverticulitis or significantly increased risk for GI perforation per investigator judgment.
  15. Conditions that could interfere with drug absorption including but not limited to short bowel syndrome.
  16. History of demyelinating disease such as Multiple Sclerosis.
  17. Subject has been a previous recipient of an organ transplant.

18. History of clinically significant medical conditions or any other reason that in the opinion of the Investigator would interfere with the subject's participation in this study or would make the subject an unsuitable candidate to receive study drug.
19. Active infection(s) requiring treatment with parenteral anti-infectives within 30 days, or oral anti-infectives within 14 days prior to the first dose of study drug.
20. History of an allergic reaction or significant sensitivity to constituents of the study drug(s) (and their excipients) and/or other products in the same class.
21. Laboratory values meeting the following criteria within the Screening period prior to the first dose of study drug:
  - Serum aspartate transaminase (AST)  $> 2 \times$  ULN;
  - Serum alanine transaminase (ALT)  $> 2 \times$  ULN;
  - Estimated glomerular filtration rate (GFR) by simplified 4-variable Modification of Diet in Renal Disease (MDRD) formula  $< 40$  mL/min/1.73m^2;

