  - Total white blood cell count (WBC)  $< 2,500/\mu\text{L}$ ;
  - Absolute neutrophil count (ANC)  $< 1,500/\mu\text{L}$ ;
  - Platelet count  $< 100,000/\mu\text{L}$ ;
  - Absolute lymphocyte count  $< 800/\mu\text{L}$ ;
  - Hemoglobin  $< 10$  g/dL.
22. History of any of the following cardiovascular conditions:
  - moderate to severe congestive heart failure (New York Heart Association class III or IV);
  - Recent (within past 6 months) cerebrovascular accident, myocardial infarction, coronary stenting;
  - Uncontrolled hypertension as defined by a confirmed systolic blood pressure  $> 160$  mmHg or diastolic blood pressure  $> 100$  mmHg;
  - Any other condition which, in the opinion of the Investigator, would put the subject at risk by participating in the protocol.

23. Clinically relevant or significant ECG abnormalities, including ECG with QT interval corrected for heart rate (QTc) using Fridericia's correction formula (QTcF) > 500 msec.

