10.3.3.2 Assessment of Potentially Clinically Significant Laboratory Values

Long-term laboratory data will be summarized based on the number and percentage of subjects meeting the criteria for potentially clinical significant laboratory values and by the accrual treatment received at the time of the event occurrence. Two sets of

summaries, namely "summary based on all study drug exposure" and "summary based on long-term study drug," will be provided following the treatment groups as described in Section 10.1.3 (similar to the analysis of long-term adverse events). In the "summary based on all study drug exposure," a subject can contribute to two treatment groups if he/she switched treatment. In the "summary based on long-term study drug," a subject will only contribute to one treatment group.

In the evaluation of potentially clinically significant laboratory values, the baseline value will be determined by the last non-missing measurement recorded on or before the date of the first dose of study drug in the corresponding treatment group (which may be different than the first dose of study drug received in the study). For example, for a subject who started on placebo and switched to Upadacitinib 15 mg QD, lab values under Upadacitinib 15 mg QD exposure would be evaluated against the baseline value defined as the last non-missing measurement recorded on or before the date of the first dose of Upadacitinib 15 mg QD.

A listing of all subjects with any laboratory determination meeting OMERACT criteria of Grade 3 or 4 will be provided by Grade. For creatine phosphokinase and creatinine, NCI CTC criteria will be used. For each of these subjects, the whole course of the respective parameter will be listed.

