J2. Cough	Transient, intermittent, occasional OTC meds relieve	Persistent, requires narcotic or other prescription meds for relief	Recurrent, persistent coughing spasms without consistent relief by meds, interferes with function	Interferes with oxygenation; debilitating

J3. Dyspnea	Subjective, transient, no interference with function	Symptomatic, intermittent or recurring, interferes with exertional activities	Symptomatic during daily routine activities, interferes with function, treatment with intermittent nasal O ₂ relieves	Symptomatic at rest, debilitating, requires constant nasal O ₂
J4. Pleuritic pain (pleurisy)	Transient, intermittent symptoms, no treatment or OTC meds relieve	Persistent symptoms, requires prescription meds for relief	Prolonged symptoms, interferes with function, requires frequent narcotic pain relief	Debilitating, requiring hospitalisation
J5. Pneumonitis (pulmonary infiltrates)	Asymptomatic radiographic changes, transient, no treatment required	Symptomatic, persistent, requiring corticosteroids	Symptomatic, requiring treatment including O ₂	Debilitating, not reversible; or requiring assisted ventilation
J6. Pulmonary function decreased (FVC or carbon monoxide diffusion capacity – DLCO)	76% – 90% of pre-treatment value	51% – 75% of pre-treatment value	26% – 50% of pre-treatment value	≤ 25% of pre-treatment value
Laboratory Data				
K. Haematology				
K1. Hgb (g/dl) decrease from pre-treatment	1.0 – 1.4	1.5 – 2.0	2.1 – 2.9, or Hgb < 8.0, > 7.0	≥ 3.0; or Hgb < 7.0
K2. Leukopenia (total WBC) × 1000	3.0 – 3.9	2.0 – 2.9	1.0 – 1.9	< 1.0
K3. Neutropenia (× 1000)	1.5 – 1.9	1.0 – 1.4	0.5 – 0.9	< 0.5
K4. Lymphopenia (× 1000)	1.5 – 1.9	1.0 – 1.4	0.5 – 0.9	< 0.5
K5. Platelets (× 1000)	75 – LLN	50 – 74.9	20 – 49.9; platelet transfusion required	< 20; recurrent platelet transfusions

L. Chemistry					
	1.1 × ULN – 11.5	11.6 – 12.5	12.6 – 13.5; or symptoms present	> 13.5; or associated coma	
L1. Hypercalcaemia (mg/dl)	1.1 × ULN – 11.5	11.6 – 12.5	12.6 – 13.5; or symptoms present	> 13.5; or associated coma	
L2. Hyperglycemia (mg/dl) Fasting	140 – 160	161 – 250	251 – 500	> 500, or associated with ketoacidosis	
L3. Hyperkalaemia (mmol/l)***	5.5 – 5.9	6.0 – 6.4	6.5 – 7.0 or any ECG change	> 7.0 or any arrhythmia	
L5. Hypocalcaemia (mg/dl)	0.9 × LLN – 7.8	7.7 – 7.0	6.9 – 6.5; or associated with symptoms	< 6.5 or occurrence of tetany	

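### Grade 3–4 laboratory counts require no worsening from baseline, so lymphocyte values already Grade 3 at entry can count as on-drug findings, mainly a problem in the long-term table

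*SAP*

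**What the plan says.** SAP 10.3.2.3 sets the short-term rule: "The criteria for potentially clinically significant laboratory values will be determined by OMERACT criteria of Grade 3 or 4". CPK and creatinine use NCI CTC grades instead. The output is the number and percentage of subjects by as-treated group and overall. The section does not restrict the count to post-baseline values, although 10.3.2.4 (liver elevations) does.

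SAP 10.3.3.2 carries the same criteria into the long-term summaries. In the summary based on all study drug exposure, "a subject can contribute to two treatment groups if he/she switched treatment". Baseline is redefined as the last value on or before the first dose of the drug concerned, and values are to be evaluated against it. No rule says that the grade must worsen.

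Protocol 5.2.2, criterion 21, excludes "Laboratory values meeting the following criteria within the Screening period prior to the first dose of study drug", and for lymphocytes the limit is below 800/µL. In SAP Appendix A the lymphopenia row, read from Grade 1 to Grade 4, is "K4. Lymphopenia (× 1000) 1.5 – 1.9 1.0 – 1.4 0.5 – 0.9 < 0.5". Protocol Appendix O prints the same bands.

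SAP 10.3.2.2 plans short-term shift tables of baseline grade against final, maximum and minimum grade. The long-term laboratory section (10.3.3) plans mean changes, these counts, liver elevations and listings, but no shift table.

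**The concern.** The lymphocyte grade is an absolute band with no baseline term. A subject at 850/µL before the first dose is already Grade 3, and an identical later value meets the criterion. The table then presents as an on-treatment abnormality something that the subject brought into the trial. Other variables behave this way wherever entry is not limited: criterion 21 sets no limit for glucose or CPK.

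Comparing safety with placebo and adalimumab is a stated objective, and these frequency tables are part of the standard safety output (SAP 10.1.1 to 10.1.3). At stake is whether a reader can take the percentage under a drug as the share of subjects who became abnormal on it. The wording is also open enough for two programmers to build different tables: one might include baseline values or ignore baseline grade, and another might not.

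**Working it through.** There is no figure in the plan to reproduce. The check sets each entry limit in criterion 21 against the printed Grade 3 band, follows one subject through the long-term rule, and then illustrates the size.

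**1. Entry limits against Grade 3**

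| Variable | Eligible at entry | Grade 3 | Overlap |
|---|---|---|---|
| Lymphocytes (×1000/µL) | ≥ 0.8 | 0.5–0.9 | Yes, 0.8–0.9 |
| Neutrophils (×1000/µL) | ≥ 1.5 | 0.5–0.9 | No |
| White cells (×1000/µL) | ≥ 2.5 | 1.0–1.9 | No |
| Platelets (×1000/µL) | ≥ 100 | 20–49.9 | No |
| Haemoglobin (g/dL), absolute part | ≥ 10 | < 8.0 | No |
| AST, ALT (× ULN) | ≤ 2 | from 3.1 (AST), 3.0 (ALT) | No |

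Only lymphocytes overlap. The certain range is 800–900/µL, because the printed bands jump from 0.9 to 1.0 and the documents give no rounding rule for 901–999/µL. The entry limit applies to screening values. Haematology is drawn again at the Baseline visit (Protocol Table 2), so a baseline value lower than the screening value is also possible.

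**2. One unchanged subject in the long-term table**

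Take a subject randomised to placebo who stays at 850/µL throughout and switches to upadacitinib at Week 26.

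- Placebo group: post-baseline values are Grade 3, so the subject is counted.
- Any-upadacitinib group: baseline is reset to the last value before the first upadacitinib dose, again 850/µL. The grade does not use baseline, so the subject is counted again.

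The subject is also in both denominators, so double counting alone need not raise a percentage. The problem is that the upadacitinib count includes a condition present before upadacitinib began.

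**3. Unequal follow-up**

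Up to Week 26 there are 8 scheduled post-baseline haematology samples (Weeks 2, 4, 8, 12, 14, 18, 22, 26). After a Week 26 switch there are 4 more in Period 1 (Weeks 30, 36, 42, 48). Period 2 adds up to 21, since 5 × 52 = 260 weeks and 260 / 12 = 21.7. That is 8 chances on placebo to record a value below the cut-off against up to 25 on upadacitinib. The percentage of subjects is not adjusted for exposure.

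**4. Size in the short-term table, illustration only**

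Let b be the share who enter at Grade 3 and record Grade 3 again after baseline, and p the new Grade 3–4 incidence in the rest. Reported rate = b + (1 − b) × p. Neither b nor p is in the documents. Assume p = 5% on placebo and 10% on upadacitinib (ratio 2.0, difference 5.0 points).

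| b | Subjects per 600 (per 300) | Placebo | Upadacitinib | Ratio | Difference (points) |
|---|---|---|---|---|---|
| 1% | 6 (3) | 6.0% | 10.9% | 1.83 | 4.95 |
| 3% | 18 (9) | 7.9% | 12.7% | 1.62 | 4.85 |
| 5% | 30 (15) | 9.8% | 14.5% | 1.49 | 4.75 |
| 10% | 60 (30) | 14.5% | 19.0% | 1.31 | 4.50 |

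For b = 3%: 0.03 + 0.97 × 0.05 = 0.0785 and 0.03 + 0.97 × 0.10 = 0.127. The difference shrinks only by the factor (1 − b).

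**The case against.** The case for leaving the rule alone has substance.

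- A reader might infer that the lymphopenia analysis among the adverse events of special interest is distorted. It is not. SAP 10.2.1.6 identifies those events by a MedDRA query on reported adverse events, 10.2 requires onset after the first dose, and Protocol 6.1.1.1 makes a laboratory abnormality an adverse event only if it leads to discontinuation or intervention or the investigator judges it one. The differences and confidence intervals planned for those events are untouched by 10.3.2.3.
- A reader might take the falling ratio as a distorted treatment comparison. The SAP plans no ratio, difference or test for these counts. Randomisation spreads entry cases across arms in the short-term tables, and the risk difference hardly moves.
- The short-term shift tables already show baseline against maximum grade, so new Grade 3–4 cases can be read off.
- Table 12 asks for a change from baseline in blood pressure, pulse and weight, but not in respiratory rate or temperature, and the liver criteria are absolute limits. The SAP has no general convention that 10.3.2.3 breaks.
- Contribution to two groups is disclosed, and the companion summary based on long-term study drug counts each subject once.
- Counting only worsening grades would drop a subject who falls from 850 to 520/µL, close to the 500/µL limit in Protocol Table 7.

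All of this stands for the short-term tables. For the long-term tables it answers less. There is no shift table, and the companion summary also lacks a worsening condition, so a placebo starter's unchanged value still appears under upadacitinib. The planned listing of each subject's whole course allows reconstruction only by hand. The point about falls within a grade is sound and shapes the fix.

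**Conclusion.** The point holds as one of reporting clarity. As written, 10.3.2.3 and 10.3.3.2 mix Grade 3 values present at entry with those that arise on drug. Lymphocytes at 800–900/µL are the certain case; glucose and CPK, which have no entry limit, are possible ones. The short-term effect is inflated percentages in all arms, recoverable from the shift tables. The long-term table based on all study drug exposure is the weaker one, because switching and unequal follow-up are not balanced by randomisation and baseline grade is not tabulated.

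The documents give no baseline lymphocyte distribution, so the size is unknown. The 1% to 10% range, the 5% and 10% incidences, and the premise that every entry case records Grade 3 again are assumptions. No efficacy result or adverse event analysis depends on this.

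**What to change.** In SAP 10.3.2.3 and 10.3.3.2:

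1. Report the number and percentage of subjects with a post-baseline Grade 3 or 4 value whose grade is worse than the applicable baseline grade. For 10.3.3.2, use the baseline already defined there for each treatment group.
2. State the denominator as subjects with both a baseline and a post-baseline value.
3. On a separate line, show subjects with baseline Grade 3 or above and a post-baseline Grade 3–4 value, so that further falls within the grade stay visible. A footnote should say that a move from Grade 3 to Grade 4 appears on both lines.
4. Keep the shift tables in 10.3.2.2 and the listing of all Grade 3–4 values.

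The cost is SAP wording, one programming condition and one extra table line. Eligibility, treatment and data collection do not change.

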10.3.2.4 Assessment of Liver Elevations

According to FDA's Guidance for Industry "Drug-Induced Liver Injury: Premarketing clinical evaluation (July 2009), when aminotransferase (AT) abnormalities indicating hepatocellular injury are accompanied by evidence of impaired hepatic function (bilirubin elevation $> 2 \times$ ULN), in the absence of evidence of biliary obstruction (i.e., significant elevation of ALP) or some other explanation of the injury (e.g., viral hepatitis, alcohol hepatitis), the combined finding (i.e., Hy's Law cases) represents a signal of a potential for the drug to cause severe DILI.

For the purpose of assessing for potential Hy's law cases, the frequencies and percentages of subjects with post baseline liver specific function test values that meet the following criteria of potential clinical interest will be summarized by "as treated" treatment group:

- $ALT \geq 3 \times ULN$
- $ALT \geq 5 \times ULN$
- $ALT \geq 10 \times ULN$

- $ALT \geq 20 \times ULN$
- $AST \geq 3 \times ULN$
- $AST \geq 5 \times ULN$
- $AST \geq 10 \times ULN$
- $AST \geq 20 \times ULN$
- $TBL \geq 2 \times ULN$
- Alkaline phosphatase $\geq 1.5 \times ULN$
- ALT and/or AST $\geq 3 \times ULN$ and concurrent TBL $\geq 1.5 \times ULN$
- ALT and/or AST $\geq 3 \times ULN$ and concurrent TBL $\geq 2 \times ULN$

10.3.3 Analysis of Long-Term Laboratory Data

10.3.3.1 Assessment of Mean Change from Baseline in Clinical Laboratory Variables

Analyses of mean change from baseline in continuous hematology, chemistry, and urinalysis variables which are measured longitudinally will be performed by visits and by "as treated" treatment group sequences as described at the end of Section 10.1.3. For each change from baseline analysis, the following summary statistics will be presented for each treatment group: sample size, baseline mean, visit mean, and the mean, standard deviation, and median of the changes from baseline. Plots of mean change from baseline by treatment group sequences over time up to Week 48 may be provided for key lab parameters.

In addition, similar analyses will be performed for percentage change from baseline in hemoglobin, LDL-C, HDL-C and triglycerides.

10.3.3.2 Assessment of Potentially Clinically Significant Laboratory Values

Long-term laboratory data will be summarized based on the number and percentage of subjects meeting the criteria for potentially clinical significant laboratory values and by the accrual treatment received at the time of the event occurrence. Two sets of

summaries, namely "summary based on all study drug exposure" and "summary based on long-term study drug," will be provided following the treatment groups as described in Section 10.1.3 (similar to the analysis of long-term adverse events). In the "summary based on all study drug exposure," a subject can contribute to two treatment groups if he/she switched treatment. In the "summary based on long-term study drug," a subject will only contribute to one treatment group.

In the evaluation of potentially clinically significant laboratory values, the baseline value will be determined by the last non-missing measurement recorded on or before the date of the first dose of study drug in the corresponding treatment group (which may be different than the first dose of study drug received in the study). For example, for a subject who started on placebo and switched to Upadacitinib 15 mg QD, lab values under Upadacitinib 15 mg QD exposure would be evaluated against the baseline value defined as the last non-missing measurement recorded on or before the date of the first dose of Upadacitinib 15 mg QD.

A listing of all subjects with any laboratory determination meeting OMERACT criteria of Grade 3 or 4 will be provided by Grade. For creatine phosphokinase and creatinine, NCI CTC criteria will be used. For each of these subjects, the whole course of the respective parameter will be listed.

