- At Week 26, all remaining subjects will be switched to blinded Upadacitinib treatment regardless of clinical response.

ADA:

- Subjects who do not achieve a $\geq 20\%$ improvement in TJC and SJC at Weeks 14, 18, or 22 compared to baseline will be switched to blinded Upadacitinib treatment.
- At Week 26, all remaining subjects who do not achieve LDA according to CDAI (LDA defined as $CDAI \leq 10$) at Week 26 will be switched to blinded Upadacitinib treatment.

Upadacitinib:

- Subjects who do not achieve a $\geq 20\%$ improvement in TJC and SJC at Weeks 14, 18, or 22 compared to baseline will be switched to blinded ADA treatment.
- At Week 26, all remaining subjects who do not achieve LDA according to CDAI (LDA defined as $CDAI \leq 10$) at Week 26 will be switched to blinded ADA treatment.

An unblinded analysis will be conducted after all subjects have completed Week 26 for the purpose of regulatory submission. To maintain integrity of the trial and avoid introduction of bias, study sites and subjects will remain blinded for the duration of Period 1. Additional unblinded analyses may be conducted after the Week 26 unblinded analysis for regulatory purposes.

Each subject will undergo a maximum of 5 scheduled visits for x-ray examination of bilateral hands and feet during Period 1 (unless unscheduled repeat imaging is needed due to failure to meet the quality requirements) at Screening, Week 26, and Week 48/Premature Discontinuation. Subjects who are non-responders (defined as those not achieving $\geq 20\%$ improvement in TJC and SJC criterion) at Week 14 and are switched to rescue therapy will have an x-ray examination at Week 14; in addition, subjects who prematurely discontinue from study drug or the study [REDACTED] will have an x-ray examination at the premature discontinuation timepoint (refer to protocol for additional details).

[figure not shown]
Joint x-rays will be sent to the central imaging vendor designated by the Sponsor. The x-rays will only be assessed by the imaging vendor for joint erosions and joint space narrowing, and will not be assessed for any other clinically significant findings that may impact a subject's health.

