10.1.3 Long-Term Safety Analysis

Long-term safety analyses include reporting of AE rate adjusted by cumulative exposure, mean change from baseline in laboratory parameters and vital sign variables, and frequency of potentially clinically significant laboratory and vital signs values.

The treatment-emergent adverse event (TEAE) rate per 100 patient-years of exposure will be presented by actual treatment received (i.e., exposed to) at the time of AE (treatment exposure for subjects switching treatments is described in Section 8.1). Listing of subjects with TEAEs by SOC and PT will be provided. Frequency tables and listings of subjects meeting criteria for potentially clinically significant vital sign values and for potentially clinically significant laboratory values will be provided by actual treatment received at the time of event.

For long-term analysis of TEAEs and potentially clinically significant laboratory or vital signs values, two sets of summaries will be provided, namely "summary based on all study drug exposure" and "summary based on long-term study drug."

Summary based on all study drug exposure:

This summary will take into account safety data under the exposure of each study drug for each subject, i.e., an all-inclusive summary. The summary will be grouped by study drug as follows (and as illustrated in the figure below):

[figure not shown]
1. Placebo

2. Any ADA 40 mg EOW

This includes ADA exposure from subjects starting on ADA 40 mg EOW and subjects rescued from Upadacitinib 15 mg QD to ADA 40 mg EOW

3. Any Upadacitinib 15 mg QD

This includes Upadacitinib 15 mg QD exposure from subjects starting on Upadacitinib 15 mg QD, subjects rescued/switched from placebo to Upadacitinib 15 mg QD, and subjects rescued from ADA 40 mg EOW to Upadacitinib 15 mg QD

UPA = upadacitinib; ADA = adalimumab; PBO = placebo; WK = week; trt = treatment

* Treatment switching may occur at Week 14, 18, 22 or 26. Treatment switching in the graph is positioned between Week 14 and Week 26 for illustration purposes.

1. Belongs to group 1: Placebo.
2. Belongs to group 2: Any ADA 40 mg EOW.
3. Belongs to group 3: Any Upadacitinib 15 mg QD.

Summary based on long-term study drug:

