10.2.2 Analysis of Long-Term Adverse Event Rates

Long-term adverse event rates will be analyzed using event rates adjusted by cumulative exposure and will be based on the actual treatment received at the time of AE occurrence. Two sets of summaries, "summary based on all study drug exposure" and "summary based on long-term study drug," respectively, will be provided following the treatment groups as described in Section 10.1.3.

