10.3.3.3 Assessment of Liver Elevations

The frequencies and percentages of subjects with post baseline liver-specific function test values that meet the following criteria of potential clinical interest will be summarized by the actual treatment received at the time of the event occurrence. Two sets of summaries, namely "summary based on all study drug exposure" and "summary based on long-term study drug," will be provided, similarly as described in Section 10.3.3.2.

- $ALT \geq 3 \times ULN$
- $ALT \geq 5 \times ULN$
- $ALT \geq 10 \times ULN$

- $ALT \geq 20 \times ULN$
- $AST \geq 3 \times ULN$
- $AST \geq 5 \times ULN$
- $AST \geq 10 \times ULN$
- $AST \geq 20 \times ULN$
- $TBL \geq 2 \times ULN$
- Alkaline phosphatase $\geq 1.5 \times ULN$
- ALT and/or AST $\geq 3 \times ULN$ and concurrent TBL $\geq 1.5 \times ULN$
- ALT and/or AST $\geq 3 \times ULN$ and concurrent TBL $\geq 2 \times ULN$

A listing of potentially clinically significant liver elevations based on criteria specified above will be provided. For each of these subjects, the whole course of the respective parameter will be listed.

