10.4.3 Analysis of Long-Term Vital Signs

Analyses of mean change from baseline in continuous vital signs variables which are measured longitudinally will be performed by visits and by "as treated" treatment group sequence as described at the end of Section 10.1.3. For each change from baseline

analysis, the following summary statistics will be presented for each treatment group: sample size, baseline mean, visit mean, and the mean, standard deviation, and median of the changes from baseline.

Long-Term Vital Sign will also be summarized based on the number and percentage of subjects meeting the criteria for potentially clinically significant vital sign values and by the actual treatment received at the time of the event occurrence. Two sets of summaries, namely "summary based on all study drug exposure" and "summary based on long-term study drug," will be provided, similarly as described in Section 10.3.3.2. In the evaluation of potentially clinically significant vital sign values, the baseline value will be determined by the last non-missing measurement recorded on or before the date of the first dose of study drug in the corresponding treatment group, similarly as described in Section 10.3.3.2.

A listing of all subjects with any vital sign values meeting the criteria for potentially clinically significant vital signs will be provided. For each of these subjects, the whole course of the respective parameter will be listed.

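### Long-term laboratory, liver and vital-sign tables set crude placebo percentages from at most 26 weeks beside active-drug percentages from up to about 5.9 years

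*SAP*

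**What the plan says.** SAP 10.1.3 defines two long-term safety summaries. The first covers all study drug exposure. Of it the SAP says "The summary will be grouped by study drug as follows", and lists Placebo, Any ADA and Any Upadacitinib. The second covers only the drug a subject stays on long term, and its five groups include no placebo group.

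Three sets of outcomes in these summaries are given as plain percentages of subjects:

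- Laboratory values (10.3.3.2): "Long-term laboratory data will be summarized based on the number and percentage of subjects meeting the criteria for potentially clinical significant laboratory values".
- Liver elevations (10.3.3.3): "The frequencies and percentages of subjects with post baseline liver-specific function test values" meeting set thresholds.
- Vital signs (10.4.3): "Long-Term Vital Sign will also be summarized based on the number and percentage of subjects" meeting set criteria.

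None has a patient-time denominator or a fixed time point. Adverse events in the same groups are handled differently (10.2.2): "Long-term adverse event rates will be analyzed using event rates adjusted by cumulative exposure".

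On the end of placebo exposure, SAP 4.2 says: "At Week 26, all remaining subjects will be switched to blinded Upadacitinib treatment regardless of clinical response". Rescue can end it sooner: "Treatment switching may occur at Week 14, 18, 22 or 26" (10.1.3). Active treatment runs through Period 1 (48 weeks) and Period 2 (up to 5 years; protocol synopsis).

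**The concern.** The percentage of subjects who ever meet a criterion grows with the time they are watched. In the all-exposure summary the design itself fixes very different times for placebo and the active drugs. A higher active percentage would be expected even if neither drug did anything, wherever abnormalities keep arising after Week 26.

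Anaemia, neutropenia, lymphopenia, CPK, creatinine and hepatic changes are among the adverse events of special interest in protocol 6.1.1.3. Their adverse-event tables would be adjusted for exposure and the matching laboratory tables would not, so the two could point in different directions for the same toxicity. The SAP puts no caveat on the long-term placebo column and does not direct placebo comparisons to the short-term tables.

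**Working it through.** The plan states no figure here to reproduce. The check asks what the tables would show with no drug effect.

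**Exposure, from the schedule** (weeks × 7 / 365.25):

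- Placebo: 26 weeks = 0.50 years at most; 14 weeks = 0.27 years if rescued at Week 14.
- Upadacitinib from baseline: 0.92 + 5 = 5.92 years at most. From a Week 26 switch: 5.42 years.
- Ratio of maxima: 5.92 / 0.498 = 11.9.

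**One subject followed for the whole time.** The documents give no event rate, so assume the same constant hazard *h* on every treatment. The expected percentage is 1 − exp(−*hT*).

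| Assumed *h* per 100 patient-years | Placebo, 26 weeks | Active, 1 y | 2 y | 5 y | 5.92 y |
|---|---|---|---|---|---|
| 1 | 0.50% | 1.00% | 1.98% | 4.88% | 5.75% |
| 2 | 0.99% | 1.98% | 3.92% | 9.52% | 11.17% |
| 5 | 2.46% | 4.88% | 9.52% | 22.12% | 25.62% |

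**Pooled groups as the SAP defines them.** Any Upadacitinib also contains switchers from placebo and ADA, and subjects who leave for ADA. With stopping rate *d*, the expected share is *h*/(*h*+*d*) × (1 − exp(−(*h*+*d*)*T*)), averaged over subgroups. Assumptions: *h* = 2 per 100 patient-years; *d* = 5% or 15% per year; randomised arms of 600, 600 and 300; three rescue patterns, with 20–50% of placebo switching at Week 14 and the rest at Week 26. For simplicity all switching falls at Week 14 or Week 26, and switcher numbers are not reduced for earlier stopping.

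Worked placebo example (40% rescued at Week 14, *d* = 5%): 0.4 × 0.53% + 0.6 × 0.98% = 0.80%.

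| Follow-up | Placebo | Any Upadacitinib | Any ADA |
|---|---|---|---|
| To Week 48 | 0.74–0.89% | 1.03–1.19% | 0.97–1.30% |
| Full 5-year extension | 0.74–0.89% | 5.3–8.1% | 5.1–7.8% |

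Within each scenario, upadacitinib over placebo is about 1.3 to 1.5 to Week 48 (for example 1.16/0.80 = 1.45) and about 7 to 10 with the full extension (for example 7.65/0.80 = 9.6).

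**If detection depends on draws rather than time.** Protocol Tables 2 and 4 schedule 8 post-baseline draws through Week 26, 12 through Week 48, and about 21 more at 12-week intervals over 5 years. With equal probability per draw, a full-term subject has 33/8 = 4.1 times the chances of a placebo subject who stays to Week 26, and 12/8 = 1.5 times to Week 48. The direction is unchanged and the long-term size is smaller.

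**Chance reversals.** Simulating 600 placebo subjects (0.42 years each) and 1,300 upadacitinib subjects with equal hazards, upadacitinib was no higher than placebo in about 41% of runs at 0.1 per 100 patient-years and 1 year of exposure. The figure was 6.5% at 1 per 100 patient-years and 1 year, and about 0% at 2 per 100 patient-years and 2 years.

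**The case against.** The best defence is that the plan already has sound placebo comparisons. The same laboratory, liver and vital-sign percentages are given for all three arms up to Week 14, before any planned switching (SAP 10.1.1), and up to Week 26 censored at switching (10.1.2), as applied in 10.3.2.3, 10.3.2.4 and 10.4.2. The Week 26 set carries some unequal censoring from rescue, but every arm is capped at the same time. The named toxicities also get exposure-adjusted rates as adverse events of special interest (10.2.2.3), with confidence intervals for rate differences (10.2.2.1). The long-term percentages carry no test or interval. All of this stands. It limits the problem to one descriptive column, but it does not make that column comparable. The adverse-event cover is partial, because many laboratory abnormalities become adverse events only at the investigator's discretion (protocol 5.3.1.1, Clinical Laboratory Tests).

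A second objection concerns the obvious remedy, a rate per 100 patient-years in every column. Placebo is sampled at 8/0.498 ≈ 16 draws per year and full-term upadacitinib at 33/5.92 ≈ 5.6. For transient abnormalities with equal probability per draw, that rate could make placebo look up to about 16/5.6 ≈ 2.9 times worse with no drug effect. This stands too, and it shapes the fix.

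**Conclusion.** The concern holds for the placebo column of the all-exposure summary in 10.3.3.2, 10.3.3.3 and 10.4.3. With no drug effect, the active percentages are expected to exceed placebo wherever abnormalities keep arising after Week 26: modestly with data to Week 48, and several-fold with the full extension. The sizes rest on the assumed hazard, rescue pattern and stopping rate. The direction rests only on the schedule and on events continuing after Week 26.

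A reader might infer more than the documents support:

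- *Upadacitinib must look worse.* This is true only in expectation. It fails if abnormalities cluster early, and chance can reverse it for rare events at short follow-up.
- *The bias also favours ADA.* Maximum follow-up is the same for both drugs, and the pooled figures can fall either way (1.19% against 1.30% in one scenario).
- *An elevenfold artefact.* That gives every upadacitinib subject the full 5.92 years and ignores switching, stopping and the thinner draws in Period 2.
- *The plan lacks a usable placebo reference.* The Week 14 and Week 26-censored tables supply one.

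**What to change.** In 10.3.3.2, 10.3.3.3 and 10.4.3, do not show crude long-term placebo percentages beside the active columns. Either of two changes would do:

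1. Drop the placebo column from the all-exposure tables and refer placebo comparisons to the Week 14 and Week 26-censored tables. This is the cheapest change.
2. Report cumulative incidence of the first qualifying value at fixed times since first dose of each drug (for example Week 26, Week 48, then yearly), censored at switch or end of exposure, with placebo shown only to Week 26. At a hazard of 2 per 100 patient-years in every arm, this gives an expected 0.99% at Week 26 in each.

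First-event incidence per 100 patient-years, using the exposure rules in SAP 8.1, may be added for the active groups alongside crude counts.

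The cost is SAP wording and table programming, with no new data. Any per-patient-year rate must carry a note that draws are denser before Week 26 than in Period 2. The fixed-time option needs a similar note for switchers: a subject starting upadacitinib at Week 26 has 4 scheduled draws (Weeks 30, 36, 42 and 48) in the first 26 weeks on drug, against 8 for one who starts at baseline.
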